8.4.2. Method of detecting AEs and SAEs, pregnancies and other events

Detection and recording of AE/SAE/pIMD/pregnancies are detailed in Section 10.3.8.

Assessment of AE/SAE intensity, causality and outcome are described in Section 10.3.9.

Open-ended and non-leading verbal questioning of participants is the preferred method of acquiring information related to an AE/SAE/pIMD/pregnancy.

8.4.2.1. Clinically significant abnormal laboratory findings

The investigator must review the laboratory report, document that he/she did so, and record any clinically relevant changes occurring during the study in the AE section of the eCRF. Clinically significant abnormal laboratory findings are those which are not associated with an underlying disease, unless judged by the investigator to be more severe than expected for the participant's condition.

- All clinically significant abnormal laboratory test values reported during the study or within 31 days after the last dose of study intervention should be repeated until the values return to normal/baseline, or until they are no longer considered significantly abnormal by the investigator or LML. Refer to Section 10.3.6 for more information on clinically abnormal laboratory assessments that qualify as an AE or SAE.
- If such values do not return to normal/baseline after an interval judged reasonable by the investigator, the etiology of the abnormal value should be identified, and the sponsor notified.

8.4.3. Regulatory reporting requirements for SAEs, pregnancies and other events

Once an investigator (or designee) becomes aware that a study participant has experienced an SAE/pIMD/pregnancy, it must be reported to GSK using the required documentation and within the timeframes mentioned in [Table 12](#). This is essential for meeting GSK legal obligations and ethical responsibilities for participant safety and the safety of a study intervention under clinical investigation.

For SAEs/pIMDs, the investigator must always provide an assessment of causality at the time of the initial report, as defined in [Section 10.3.9.2](#).

Local regulatory requirements and sponsor policy for preparation of an investigator safety report of Suspected Unexpected Serious Adverse Reactions (SUSAR) must be followed. These reports will be forwarded to investigators as necessary.

The sponsor has the legal responsibility to notify local authorities/regulatory agencies about the safety of an investigational study intervention. The sponsor will comply with country-specific regulatory requirements related to safety reporting to the regulatory authority, IRB/IEC and investigators.

Refer to [Section 10.3.10](#) for further details regarding the reporting of SAEs/pIMDs/pregnancies.

Table 12 Timeframes for submitting SAE, pIMD, pregnancy and other events reports to GSK

Type of Event	Initial Reports		Follow-up of Relevant Information on a Previous Report	
	Timeframe	Documents	Timeframe	Documents
SAEs	24 hours*	electronic Expedited Adverse Events Report	24 hours*	electronic Expedited Adverse Events Report
Pregnancies	24 hours*	electronic pregnancy report	24 hours*	electronic pregnancy report
pIMDs	24 hours** ##	electronic Expedited Adverse Events Report	24 hours*	electronic Expedited Adverse Events Report

*Timeframe allowed after receipt or awareness of the information by the investigator/site staff.

**Timeframe allowed once the investigator determines that the event meets the protocol definition of a pIMD.

##The investigator will be required to confirm review of the SAE/pIMD causality by ticking the 'reviewed' box in the electronic Expedited Adverse Events Report within 72 hours of submission of the SAE/pIMD.

8.4.4. Treatment of AEs

Any medication administered for the treatment of an SAE/pIMDs should be recorded in the Expedited Adverse Event Report of the participant's eCRF page/screen (refer to Section 10.3.10.1).

8.4.5. Participant card

The investigator (or designee) must provide the participant with a “participant card” containing information about the clinical study. The participant must be instructed to always keep the participant card in his/her/their possession for the duration of the study. In an emergency, this card serves to inform the responsible attending physician that the participant is in a clinical study and that relevant information may be obtained by contacting the investigator or his/her back-up.

8.4.6. Medical device deficiencies

The study intervention *Engerix-B* and *Fendrix* is a combination product constituted of a device and biologic product (e.g., pre-filled syringes). Refer to the [Glossary of terms](#) for the definition of combination product and medical device deficiency.

8.4.6.1. Detection, follow-up and prompt reporting of medical device deficiency

The investigator is responsible for the detection, documentation and prompt reporting of any medical device deficiency occurring during the study to GSK. This applies to any medical device provided for the conduct of the study.

Device deficiencies will be reported to GSK within 24 hours after the investigator determines that the event meets the protocol definition of a device deficiency. Refer to Section 10.6 for definitions and details on recording and reporting of these events.

The investigator will ensure that follow-up includes any additional investigations to elucidate the nature and/or related of the device deficiency to the incident. Follow-up applies to all participants, including those who discontinue study intervention or the study.

[figure not shown]
New or updated information will be recorded on the originally completed form with all changes signed and dated by the investigator and reported to GSK within 24 hours.

8.4.6.2. Regulatory reporting of medical device deficiency when used as combination product

The investigator will promptly report all device deficiencies occurring with any medical device provided for use in the study to GSK. GSK has a legal responsibility to notify appropriate regulatory authorities and other entities about safety information linked to medical devices being used in clinical studies. Refer to Section 10.6 for details of reporting.

The investigator, or responsible person according to local requirements (e.g., the head of the medical institution), will comply with the applicable local regulatory requirements relating to the reporting of device deficiencies to the IRB/IEC.

CC1

8.9. Immunogenicity assessments

Immunogenicity is described in Section 8.1.

8.10. Health outcomes

Not applicable for this study.

9. STATISTICAL CONSIDERATIONS

9.1. Statistical hypotheses

No confirmatory statistical hypotheses are to be tested. All analyses are descriptive. The use of these descriptive analyses will be limited to hypotheses generation or to supportive analyses of other confirmatory analyses or hypotheses generation.

9.2. Analysis sets

Table 14 Analysis sets

Analysis Set	Description
Screened	All participants who were screened for eligibility.
Enrolled	All participants who entered the study (who were randomized or received study intervention or underwent a post-screening procedure). NOTE: Screening failures (who never passed screening even if rescreened) and participants screened but never enrolled into the study (i.e., met eligibility but not needed) are excluded from the Enrolled Set as they did not enter the study.
Exposed	All participants who received at least 1 dose of the study intervention. Analysis per group using the Enrolled Set is based on the administered intervention.
Per-Protocol	All eligible participants who received all doses as per protocol, had immunogenicity results post-dose, complied with dosing/blood draw intervals, without intercurrent conditions that may interfere with immunogenicity and without prohibited concomitant medication/vaccination.
CCI	

9.2.1. Criteria for elimination from analysis

If the participant meets one of the criteria mentioned below or ones listed in Section 7.1.1, he/she may be eliminated from Per-Protocol analysis.

Participants may be eliminated from the Per-Protocol Set for immunogenicity if, during the study, they incur an intercurrent medical condition that could alter their immune response (i.e., varicella, HIV, lymphoma) or are confirmed to have an alteration of their initial immune status. For further details on criteria for elimination from Per-Protocol set, refer to the Statistical Analysis Plan.

9.3. Statistical analyses

The SAP will be finalized prior to the First Subject First Visit and it will include a more technical and detailed description of the statistical analyses. This section is a summary of the planned statistical analyses.

The analyses will be descriptive with the aim to characterize the safety/reactogenicity and immunogenicity of the vaccine groups.

Any deviation(s) or change(s) from the original statistical plan outlined in this protocol will be described and justified in the final clinical study report (CSR).

9.3.1. Primary endpoints analyses

The analysis of the primary objective will be performed on the Exposed Set (ES).

Endpoint description	Analysis set	Statistical analysis methods
Reactogenicity and Safety	Exposed	
Descriptive statistics:
 
 Percentage of participants with solicited administration site and systemic AEs within 14 days (Day 1 till Day 14) and severity grading will be tabulated with exact 95% CI for each group after Dose 1 and Dose 2 of the study intervention and overall. Descriptive statistics of duration of solicited AEs (administration site and systemic) will be tabulated for each group after Dose 1 and Dose 2 of the study intervention and overall. Percentage of participants with any unsolicited AEs within 31 days (Day 1 till Day 31) and severity grading will be tabulated with exact 95% CI for each group after Dose 1 and Dose 2 of the study intervention and overall. Percentage of participants with SAEs, related SAEs, MAEs and AEs leading to study withdrawal throughout the entire study period will be tabulated with exact 95% CI for each group. Percentage of participants with pIMDs throughout the entire study period will be tabulated with exact 95% CI for each group. Descriptive statistics of the absolute values and changes in hematology and biochemical parameters from baseline at each protocol specified timepoints will be tabulated for each group. Percentage of participants with abnormal laboratory parameter values will be tabulated with exact 95% CI for each group pre-vaccination, after Dose 1 and after Dose 2 of the study intervention and overall.

AE = adverse event; **CI** = confidence interval; **SAE** = serious adverse event; **MAE** = medically attended event;

pIMD = potential immune-mediated disorder.

9.3.2. Secondary endpoints analyses

The analysis of the secondary objective will be performed on the Per-Protocol Set (PPS). If 5% or more of the vaccinated participants are eliminated from the PPS at one timepoint, an additional sensitivity analysis will be performed on the ES.

Endpoint description	Analysis set	Statistical analysis methods
Immunogenicity	Per-Protocol	
Descriptive statistics:
 
 Anti-HBs antibody GMCs and their 95% CI will be tabulated and represented graphically for each group at each timepoint. GMCs ratios, their 95% CI and related p-value for difference will be tabulated for post-Dose 1 and Dose 2 for all pairwise comparisons between groups. 
CCI [REDACTED]
 
 Antibody concentrations will be displayed using reverse cumulative curves for each protocol defined timepoint. Percentage of participants above seroconversion and seroprotection thresholds will be tabulated with exact 95% CI for each group at each protocol specified timepoint. Seroconversion and seroprotection rates will be compared, and the 95% CI and related p-value for the difference will be tabulated for post-Dose 1 and Dose 2 for all pairwise comparisons between groups. CCI [REDACTED]

GMC = geometric mean concentration; CI = confidence interval; ANCOVA = Analysis of Covariance

[figure not shown]

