## VERSION HISTORY

SAP Version	Approval Date	Protocol Version (Date) on which SAP is Based	Change	Rationale
SAP	12 Sep 2022	Amendment 1 (10 August 2022)	Not Applicable	Original version
SAP Amendment 1	22 May 2023	Amendment 2 (01-Mar-2023)	CCI	
SAP Amendment 2	11 Dec 2023	Amendment 3 (17-Nov-2023)	Amendment of Section 5 to address changed target sample size and minor adjustments in Sections 3 and 4	Protocol Amendment 3 change in target sample size
SAP Amendment 3	28 Jun 2024	Amendment 3 (17-Nov-2023)	Amendment on Section 4.2.1 to reference to the newly added Appendix 6.2.  Addition of Appendix 6.2.	Inclusion of Electronic Clinical Outcome Assessment (eCOA) Compliance analysis description

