### ***Secondary estimand***

The secondary clinical question of interest is to assess the humoral immune response in all eligible participants who received all doses as per protocol, had immunogenicity results post-dose, complied with dosing/blood draw intervals, without intercurrent conditions that may interfere with immunogenicity and without prohibited concomitant medication/vaccination (i.e., the Per Protocol Set [PPS]).

The estimand is described by the following attributes:

- Population: PPS. If in any study group, the percentage of vaccinated participants with serological results excluded from the PPS is more than 10%, a second analysis based on the ES will be performed to complement the PPS analysis.
- Treatment condition: 5 treatment groups as described in [Table 1](#).
- Variable / endpoint:
  - Anti-hepatitis B surface antigen (HBs) antibody (Ab) concentrations at Day 1, Day 31, Day 61 and Day 361.
  - Anti-HBs seroconversion and seroprotection status at Day 31, Day 61 and Day 361.
- Summary measure:
  - Geometric Mean Concentrations (GMC) of Anti-HBs Ab.
  - Percentage of participants above seroconversion and seroprotection thresholds.
    - Participants not having results for a specific visit (but being part of the PPS) will not be considered in the denominator, no imputation will be done (see Section [6.3.2](#) for details).

[figure not shown]
CCI

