#### **3.1.3. Elimination from Per-protocol Set (PPS)**

A participant will be excluded from the per-protocol set (PPS) for analysis of humoral immunogenicity in the following manner:

- For codes 800, 900, 1030, 1050 and 2010: participants will be eliminated for all visits.
- For codes 1040, 1070, 1080, 1090, 2040, 2050 and 2080: participants will be eliminated from the specific visit at which the condition is met and onwards.
- For codes 2090, 2100, 2110, 2120: participants will be eliminated at the specific visit at which the condition is met.

CCI

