2080	Participants did not comply with vaccination schedule: 
 
Number of days between Visit 1 and Visit 4 is outside [21-42 days] for all study groups
 
Number of days between Visit 4 and Visit 8 is outside [136-164 days], for HBs-alum group
 
	From the specific visit the condition is met.	PPS
2090	Participants did not comply with blood sample schedule (any of the below options): 
 
Number of days between Visit 1 and Visit 4 is outside [21-42] days
 
Number of days between Visit 4 and Visit 7 is outside [21-42 days]
 
Number of days between Visit 7 and Visit 9 is outside [286-314 days]
 
	At the specific visit (4 or 7 or 9) the condition is met	PPS
2100	Serological antibody results not available.	At the specific visit (1 or 4 or 7 or 9) the condition is met	PPS

Code	Condition under which the code is used	Visit when it is applicable	Applicable for analysis set/endpoint
2110	Blood sample for serological antibodies available but not yet tested (main analysis)	At the specific visit (1, or 4, or 7, or 9) the condition is met	PPS
2120	Issues in the lab results that are not related to handling of lab samples (Eg: Hemolysis, calibration of instruments) Unreliable released data as a result of confirmed sample mismatch or confirmed inappropriate sample handling at lab	At the specific visit the condition is met	PPS

CCI

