## 4.8. Changes to Protocol- Defined Analyses

Not applicable.

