### **6.3.2. Handling of missing data**

#### **6.3.2.1. Missing data related to immunological outputs (e.g., if a participant misses a visit),**

- If there is a small proportion of missing data(<10%), missing or non-evaluable measurements (e.g., for a given participant at a given timepoint) will not be replaced. Therefore, analyses will exclude these participants.

- If there is a large proportion of missing data ( $\geq 10\%$ ), there may be an assessment to determine if the data are missing due to systematic issues or not (e.g., if not, missing completely at random). The result of this assessment will determine the mitigation strategy (e.g., we may impute data if deemed necessary).

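### Protocol and SAP set different triggers for the Exposed Set immunogenicity analysis, so following the SAP can skip an analysis the protocol requires

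*Protocol*

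**What the plan says.** Protocol 9.3.2 analyses the secondary objective on the PPS and adds an ES sensitivity analysis "If 5% or more of the vaccinated participants are eliminated from the PPS at one timepoint". It does not say whether the percentage is per group or over all groups.

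The Population attribute of the secondary estimand in SAP 1.1 sets the trigger for the same analysis differently: "If in any study group, the percentage of vaccinated participants with serological results excluded from the PPS is more than 10" per cent, an ES analysis will complement the PPS one. No timepoint is named.

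SAP 4.8, "Changes to Protocol- Defined Analyses", is marked not applicable. SAP 4.3 names only the PPS for this objective.

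Two further provisions affect the counting. SAP 3.1.3 makes some exclusions visit-specific: "For codes 2090, 2100, 2110, 2120: participants will be eliminated at the specific visit at which the condition is met". One of these, code 2100 in SAP Table 4, is "Serological antibody results not available". A missing result is therefore itself a PPS elimination.

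**The concern.** Both sentences govern the same repeat analysis of the same endpoints. A programming team working from the SAP would apply the SAP rule and could omit an analysis that the protocol says will be done.

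The ES analysis is the only legible planned repeat of the GMC and seroprotection results that brings back excluded participants who have serology. It is the reader's check on whether PPS exclusions shaped the comparison between adjuvants. With two triggers in force, the decision to run it can also be made after the data are seen. The rationale for Protocol Amendment 4 shows that the Day 61 immunogenicity results were already known by then.

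**Working it through.** The documents give no derived figure on this point, so there is none to reproduce. The check compares the two rules by counting, then by probability.

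**Inputs.** Five groups of 23 to 30 (Protocol 4.2.1 and 9.5), so 115 to 150 in total. Protocol cut-off: at least 5%. SAP cut-off: more than 10%.

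**Smallest counts that fire, if everyone has serology**

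| Rule | 23 per group | 30 per group |
|---|---|---|
| Protocol, overall | 0.05 × 115 = 5.75, so 6/115 (5.2%) | 0.05 × 150 = 7.5, so 8/150 (5.3%) |
| Protocol, within a group | 0.05 × 23 = 1.15, so 2/23 (8.7%) | 0.05 × 30 = 1.5, so 2/30 (6.7%) |
| SAP, any group | more than 2.3, so 3/23 (13.0%) | more than 3.0, so 4/30 (13.3%) |

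**Protocol fires on either reading, SAP does not.** Two exclusions in every group of 23 give 10/115 = 8.7% overall and 2/23 = 8.7% in each group. Three in every group of 30 give 15/150 = 10.0% overall and 3/30 = 10.0% in each group. Neither exceeds 10%.

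**Effect of missing serology.** Suppose three of 23 are eliminated in every group, one of the three for lack of a result. The protocol counts 15/115 = 13.0%. The SAP, counting participants with results, sees 2/22 = 9.1% in each group and does not fire.

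**The reverse, where only the SAP fires.** Three exclusions in one group of 23 and none elsewhere are 3/115 = 2.6% overall, below the protocol cut-off. On the within-group reading this needs SAP exclusions to be counted across visits: a different participant at each of Visits 4, 7 and 9 is 1/23 = 4.3% each time but 3/23 = 13.0% in total.

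**Chance of a skip.** Let X1 to X5 be independent Binomial(n, q) exclusion counts at one timepoint, all participants with serology, and let c be the smallest SAP count (3 or 4). The chance that the protocol fires and the SAP does not is:

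- overall reading: P(sum of the counts ≥ 6 or 8, and every count < c), by exact convolution of the five distributions;
- any-group reading: P(X < c)^5 − P(X ≤ 1)^5.

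For example, with n = 23 and q = 0.05 the any-group figure is 0.5737 − 0.1448 = 0.4289. The documents give no legible exclusion rate, so q is assumed and a range is shown.

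| q | Overall, n = 23 | Overall, n = 30 | Any group, n = 23 | Any group, n = 30 |
|---|---|---|---|---|
| 2% | 1.3% | 0.8% | 27.8% | 46.0% |
| 5% | 15.8% | 24.4% | 42.9% | 67.9% |
| 8% | 11.9% | 22.4% | 17.9% | 29.4% |
| 12% | 1.9% | 3.2% | 2.2% | 3.4% |
| 15% | 0.3% | 0.3% | 0.3% | 0.3% |

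The reverse (SAP only, overall reading) has probability 3.6%, 6.7%, 1.8%, 0.1% and 0.01% at 23 per group, and 1.1%, 3.6%, 0.8%, 0.02% and under 0.01% at 30.

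**What a skipped analysis could have shown.** At one timepoint with full serology, the SAP stays silent with at most 2 of 23 or 3 of 30 excluded per group. A seroprotection rate could then move at most from 21/21 to 21/23 (8.7 points) or from 27/27 to 27/30 (10.0 points). If the returning participants differ tenfold from the rest (assumed), the GMC moves by a factor of 10^(2/23) = 1.22 or 10^(3/30) = 1.26.

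**The case against.** Both sentences are if-then statements, and neither forbids the ES analysis when its own condition fails. A team that runs it when either trigger fires complies with both documents. That is right, and it is why the fix is cheap. It does not help a team following the SAP alone, which is how analyses are normally programmed.

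Protocol 9.3 calls itself a summary and leaves technical detail to the SAP. However, a higher cut-off at a different level is a different rule, not an elaboration. The same section says that "change(s) from the original statistical plan outlined in this protocol will be described and justified in the final clinical study report", and SAP 4.8 lists no change.

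Version lag or redaction could explain the mismatch. Under "Protocol Version (Date) on which SAP is Based" the current SAP cites Amendment 3, while the protocol is at Amendment 4. One row of the Amendment 4 change list is redacted, and so is SAP secondary-analysis text after 4.3.1.2. It therefore cannot be shown that SAP 4.8 was wrong when approved, and other sensitivity analyses may be hidden. The two legible triggers still disagree.

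SAP 6.3.2.1 has its own 10% rule, but it concerns missing data and possible imputation: at or above that level, "there may be an assessment to determine if the data are missing due to systematic issues or not". It does not settle when the ES analysis is run.

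The SAP denominator could also be parsed as all vaccinated participants, counting those whose results are excluded. The missing-serology example then gives 2/23 = 8.7% instead of 9.1%, with the same outcome.

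The probabilities depend heavily on the assumed rate. The largest need the any-group reading, although the protocol names no group and the overall reading is the plainer one; on that reading the largest tabulated value is 24.4%. They also assume full serology and a single timepoint, so they are not study-level chances. Participants under code 2100 have no result to restore, so some triggers that only the protocol meets would add few or no observations. These limits stand and keep the point modest.

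**Conclusion.** The concern holds. The current protocol and SAP give different triggers for one analysis, and plausible exclusion patterns oblige it under the protocol, on either reading, but not under the SAP. The disagreement is concentrated at exclusion rates of roughly 5% to 8% on the overall reading, and extends down to 2% on the any-group reading. It has nearly vanished by 15%. These ranges rest on assumed, independent and equal exclusion rates across groups.

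The impact is limited. The endpoint is secondary and all analyses are descriptive; alpha, power and the primary safety analysis are unaffected. At one timepoint with full serology, a skipped analysis would restore at most two or three participants per group. This should be corrected, but it does not threaten the trial's main conclusions.

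**What to change.** In the SAP, plan the ES immunogenicity tables (exposed participants with a result) beside the PPS tables at each timepoint, unconditionally. This satisfies both triggers on every reading and removes any choice made after results are known. For Day 61 the edit would be retrospective and should be labelled so; for Day 361, whether it is prospective depends on what had been seen when the SAP is changed.

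Alternatively, put one trigger in both documents and state its cut-off, its level (per group or overall), its timepoint, and whether participants without serology count in the denominator.

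Either way, record the difference in SAP 4.8 and describe and justify it in the clinical study report.

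The cost is one extra set of immunogenicity tables for at most 150 participants and wording changes in SAP 1.1 and 4.8, plus a protocol wording change if 9.3.2 is edited.
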